2.1. Study Rationale

Currently, lyophilized albiglutide and the diluent are provided in a DCC, single-dose pen injector, requiring reconstitution prior to use. A liquid formulation of albiglutide will enable the commercialization of a liquid product in a single dose, ready-to-use prefilled syringe in an auto-injector. To support the development of the liquid auto-injector product, Study 201287, a healthy volunteer bioequivalence study will be conducted as the first component of the comparability assessment and the proposed study, Study 200952, will be conducted as the final component of the overall comparability assessment.

Extensive release and characterization testing has been utilized in studies to establish the comparability between samples of the liquid product and commercial lyophilized product. These studies were performed to evaluate the relevant differences in the quality attributes of the liquid and lyophilized products. However, non clinical studies are not suitable for predicting clinically relevant comparability of immunogenicity potential.

The albiglutide lyophilized products has been evaluated in an international program of studies involving approximately 9000 subject-years of overall exposure to date (including over 4000 subject-years of exposure to albiglutide) and has been found to have a favorable benefit:risk profile, including a low immunogenicity profile. In the clinical program with the lyophilized product, a low incidence (4.4%) of ADA was detected. Antibodies were non-neutralizing and mostly low titer and transient in nature. None of the antibodies impacted the pharmacokinetic (PK), PD or efficacy of the drug. There was a higher frequency of ISRs in antibody positive subjects, however most subjects with an ISR (including those ISRs classified as serious) were antibody negative. There was no apparent relationship between antibody positive status and other AEs that could be attributed to albiglutide.

This repeat-dose study in T2DM patients will determine if there are any clinically relevant differences between liquid drug product stored under recommended storage conditions to lyophilized drug product with respect to efficacy, safety, tolerability and PD response. Specifically, the immunogenicity potential (e.g., incidences of ADA) and ISRs will be evaluated as part of the overall safety assessment in this study.

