9.4.2. Secondary Analyses

The evaluation of the safety and tolerability as assessed by immunogenicity and ISRs of albiglutide liquid drug product and the lyophilized drug product will be provided by reporting the event rates, and the associated 95% CI.

The overall general safety and tolerability of albiglutide liquid drug product versus lyophilized drug product will be evaluated in tabular and/or graphical format and summarized descriptively.

AEs and SAEs, physical examinations, clinical laboratory evaluations, vital sign measurements, and 12-lead electrocardiogram will be summarized by treatment group. For continuous variables, these summaries will include sample size, mean, median, standard deviation (and/or standard error), minimum, and maximum. For categorical variables, the summaries will include frequencies and corresponding percentages. The exposure-adjusted incidence rate will also be calculated as the number of events in a given period divided by the total person time on treatment of subjects at risk within the same period. The exposure-adjusted incidence rate will be expressed as an annualized rate expected. No inferential testing will be performed on the safety variables. Hypoglycemic events will be analyzed separately from other AEs. All hypoglycemic events will be classified as severe, documented symptomatic, asymptomatic, probable symptomatic, and pseudohypoglycemia, as defined in Section 7.4.9.

AEs will be coded using MedDRA. AEs will be summarized in various subsets, including on therapy AEs, related AEs, AEs leading to treatment discontinuation or withdrawal from study, SAEs, fatal AEs, etc. AEs will also be summarized by maximum intensity (mild, moderate, and severe).

Anti-albiglutide antibody results will be summarized by treatment group. In addition, the number and percentage of subjects with positive results along with the antibody titer values will be provided by visit.

The secondary endpoint FPG change from baseline at Week 26 will be analyzed using MMRM without imputation.

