8.2.2. Injection Site Reactions

Injection site reactions are reported by the investigators on the eCRF. The number and percentage of subjects with injection site reactions and 95% confidence intervals of the proportions will be presented by treatment group. In addition, the time to first occurrence of an injection site reaction will be analyzed and presented in a manner identical to that described for the first occurrence of a GI event in Section 8.2.7.5.

The number and percentage of subjects reporting injection site reactions at each study week will be presented by treatment group. Each week will include those subjects with the onset of an injection site reaction during that particular week as well as those subjects with injection site reactions from previous weeks that have not resolved. The incidence of injection site reactions will be plotted over time. Various characteristics of injection site reactions at the event level and subject level will be summarized.

A by-subject listing of injection site reactions will also be produced.

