8.2.3. Immunogenicity

Serum for antidrug antibody testing will be obtained from all subjects before administration of study treatment at Week 0, 2, 4, 8, 12, 16, 20, 24, 26/early withdrawal and at follow-up (if applicable), according to the Time and Events Table in [Appendix 2](#). The presence of anti-albiglutide antibodies will be assessed using a validated enzymelinked immunosorbent assay. The assay involves screening, confirmation, and titration steps (tiered-testing approach). Confirmed positive samples will be titrated to obtain the titre of antibodies and tested for GLP-1 and albumin cross-reactivity, as well as for albiglutide neutralizing activity. Samples positive for both anti-GLP-1 antibodies and drug neutralizing antibodies may be tested for GLP-1 neutralizing activity.

Anti-albiglutide antibody results will be analyzed by treatment arm, visit, and study period for the safety population. For subjects with positive anti-albiglutide antibody results, the number and percentage with positive albiglutide neutralizing antibody results, positive anti-GLP-1 antibody results, and positive anti-albumin antibody results will be provided separately at each assessment. The 95% confidence intervals for the proportions of the positive immunogenicity results will be calculated using exact binomial method, assuming a simple binomial distribution. Antibody titers will be summarized using descriptive statistics. Individual immunogenicity data, including antibody titers, will be listed for each subject.

Additionally, in the case of severe allergic reactions that include anaphylaxis, angioedema, or other severe potential hypersensitivity reactions, three 1-mL serum samples should be obtained for immunogenicity testing (within 24 hours of the event if possible) and sent to the central laboratory for immediate distribution to a contracted testing facility for specific immunological testing (albiglutide specific IgE and other tests,

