8.2.7.5. Gastrointestinal (GI) Events

A summary of the number and percentage of subjects with GI events (specifically, AEs coded to the MedDRA SOC of gastrointestinal disorders) will be reported by treatment

group and therapeutic phase (pre-, on-, or post-therapy). Also, summaries of on-therapy GI events that lead to withdrawal of active treatment, treatment-related and serious GI events (including those that do not necessarily lead to withdrawal of active treatment) will be presented separately by treatment group.

For each subject, the time to first occurrence of a GI event is calculated as the number of days between the randomization date and the date of onset of the first on-therapy GI event plus 1. Subjects who do not experience any GI events will be censored at the last dose date + 25 days. The median time to first occurrence of a GI event as well as the Kaplan-Meier probability of first occurrence of a GI event at various time points will be presented for each treatment group.

The prevalence of GI events will be reported and plotted by treatment group.

The number and percentage of subjects reporting nausea at each study week will be presented by treatment group. Each week will include those subjects with onset of nausea during that particular week and also those subjects with nausea that started during a previous week but has not resolved. The prevalence of nausea will also be plotted over time. Similar summaries and plots will be presented for subjects reporting events of diarrhea and also separately for subjects reporting events of vomiting. In addition, a combined summary and accompanying plot of the number and percentage of subjects reporting events of nausea and/or vomiting will be presented.

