11.4. Appendix 4: Treatment Periods

For classifying AEs (including hypoglycemic events), the therapy periods will be defined as:

- **Pre-therapy:** The onset date of the AE is before the start date of randomized study medication. If the onset date of the AE is on the start date of randomized study medication, the AE will be considered as on-therapy.
- **On-therapy:** The onset date of the AE is on or after the start date of randomized study medication and within 25 days after the date of last dose.
- **Post-therapy:** The onset date of the AE is more than 25 days after the last date of randomized study medication.

For immunogenicity data and other safety parameters that are assessed prior to administration of randomized study medication on dosing days, the therapy periods will be defined as:

- **Pre-therapy:** The assessment date is on or before the start date of randomized study medication.
- **On-therapy:** The assessment date is after the start date of randomized study medication and within 25 days after the date of last dose.
- **Post-therapy:** The assessment date is more than 25 days after the last date of randomized study medication.

For an AE with an incomplete start date where the year and month are present while the day is missing, or where the year is present while both month and day are missing, the date is imputed in a dynamic way consistent with the partial date information so that the resulting AE therapy period assignment based on the imputed date is the most conservative possible, where the order from the most to the least conservative is: on-therapy phase > post-therapy phase > pre-therapy. Note that if the AE stop date is present, then the imputed start date will always be on or prior to the stop date.

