3.143.	Safety		On-therapy Injection Site Reaction over Time		
3.144.	Safety		Summary Characteristics of On-therapy Injection Site Reactions		
3.151.	Safety		On-therapy and Post-therapy Liver Events Identified by a Customized MedDRA Query		
3.161.	Safety		On-therapy and Post-therapy Pancreatitis and Pancreatic Cancer		
3.162.	Safety		On-therapy and Post-therapy Adjudicated Pancreatitis Events		
3.171.	Safety		On-therapy and Post-therapy Atrial Fibrillation and Atrial Flutter Adverse Events		
3.181.	Safety		On-therapy and Post-therapy Pneumonia Adverse Events Reported by the Investigator		

Safety : Tables					
No.	Population	IDSL / TST ID / Example Shell	Title	Programming Notes	Deliverable [Priority]
3.182.	Safety		On-therapy and Post-therapy Pneumonia Adverse Events Identified by a Customized MedDRA Query		
3.191.	Safety		On-therapy and Post-therapy Diabetic Retinopathy Adverse Events		
3.201.	Safety		On-therapy and Post-therapy Appendicitis Adverse Events		
3.211.	Safety		On-therapy and Post-therapy Malignant Neoplasm Adverse Events Identified by a Customized MedDRA Query		
Lab Assessments					
3.221.	Safety		Change from Baseline in Hematology by Visit		
3.222.	Safety		Change from Baseline in Chemistry by Visit		
3.223.	Safety		Hematology Values of Clinical Concern by Visit		
3.224.	Safety		Chemistry Values of Clinical Concern by Visit		
3.225.	Safety		Liver Function Tests of Clinical Concern by Visit		
3.226.	Safety		Shift in Hematology by Visit		
3.227.	Safety		Shift in Chemistry by Visit		
3.228.	Safety		Urinalysis by Visit		
Vital Signs					
3.231.	Safety		Change from Baseline in Vital Signs by Visit		
3.232.	Safety		Vital Signs of Clinical Concern by Visit		
3.233.	Safety		Shift in Vital Signs of Clinical Concern by Visit		
[ECG]					
3.341.	Safety		Change from Baseline in ECG Values by Visit		
3.342.	Safety		ECG Values of Clinical Concern by Visit		

Safety : Tables					
No.	Population	IDSL / TST ID / Example Shell	Title	Programming Notes	Deliverable [Priority]
3.343.	Safety		Overall ECG Interpretations by Visit		
3.344.	Safety		Shift in ECG Values of Clinical Concern from Baseline to Week 26		
3.345.	Safety		ECG QTcF and QTcB Results of Notable Abnormalities at any time post-baseli		
Immunogenicity					
3.351.	Safety		Positive Immunogenicity Results for Anti-Albiglutide Antibody Positive Subjects by Visit		
3.352.	Safety		Positive Immunogenicity Results for Anti-Albiglutide Antibody Positive Subjects by Therapy Phase		

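### ADA and injection site reactions are to be reported per arm only, with no estimate of the difference between products and no rule for treatment-emergent ADA

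*SAP*

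**What the plan says.** Protocol 2.1 sets a comparative purpose: "This repeat-dose study in T2DM patients will determine if there are any clinically relevant differences between liquid drug product" and the lyophilized product. The same paragraph names ADA and ISRs for specific evaluation. It follows a statement that non-clinical studies cannot predict comparable immunogenicity.

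The planned outputs are these.

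- **ISRs (SAP 8.2.2; Tables 3.141–3.144; Figure 3.21).** "The number and percentage of subjects with injection site reactions and 95% confidence intervals of the proportions will be presented by treatment group". Time to first ISR borrows the method of SAP 8.2.7.5, where the "Kaplan-Meier probability of first occurrence of a GI event at various time points will be presented for each treatment group". Weekly counts and event characteristics are added.
- **ADA (SAP 8.2.3; Tables 3.351–3.352; Figure 3.61).** "Anti-albiglutide antibody results will be analyzed by treatment arm, visit, and study period for the safety population". The interval is one-sample: "The 95% confidence intervals for the proportions of the positive immunogenicity results will be calculated using exact binomial method, assuming a simple binomial distribution". Titers are summarized, and individual results are listed (Listing 151).
- **Periods (SAP 11.4).** An immunogenicity result is on-therapy when "The assessment date is after the start date of randomized study medication and within 25 days after the date of last dose". A sample on or before the first dose date is pre-therapy. Table 3.352 is titled "Positive Immunogenicity Results for Anti-Albiglutide Antibody Positive Subjects by Therapy Phase".
- **Testing.** Protocol 9.4.2 asks for event rates with 95% CIs and adds: "No inferential testing will be performed on the safety variables".

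The SAP defines treatment-emergent for adverse events (8.2.4.2) but not for ADA. Protocol Appendix 7 plans a testing report that gives the incidence of immunogenicity, without a rule for counting it.

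**The concern.** There are two linked gaps.

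First, the question is whether liquid differs from lyophilized, but the outputs answer what the rate is in each arm. A reader of the report would not learn how large an increase with the liquid product the data exclude. Comparing two separate intervals by eye is a poor substitute, because overlapping intervals can coexist with a difference whose own interval excludes zero.

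Second, a subject who is ADA positive at Week 0 and again at Week 2 is pre-therapy positive and on-therapy positive. Table 3.352 would show baseline positives in aggregate. Nothing described says, subject by subject, which on-therapy positives were new. The table shells are not shown, so this rests on the text and the table titles.

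At stake are two secondary safety endpoints that the protocol picks out, and the risk that the ADA numerator is chosen after unblinding.

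**Working it through.** **The plan's own figure.** The only sample size is for HbA1c (Protocol 9.2.1): margin 0.4, SD 1, true difference 0, one-sided alpha 0.025, power 90%. The normal approximation gives 2 × (1.960 + 1.282)² × 1² / 0.4² = 131.3, so 132 per arm. The noncentral t gives 90.1% power at 133, so the stated 133 reproduces. The documents give no precision for ADA or ISRs, so what follows is illustrative, at the planned 150 per arm.

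**1. Per-arm intervals against a difference interval (ADA).** Protocol 2.1 gives 4.4% and Table 2 of Protocol 4.6.1 about 5%, so take 7/150 = 4.7% on lyophilized. The difference interval is Newcombe's, built from Wilson limits (l, u) for each arm:

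- lower = d − √[(p₁ − l₁)² + (u₂ − p₂)²]
- upper = d + √[(u₁ − p₁)² + (p₂ − l₂)²]

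Example, 17 v 7. The rates are 11.33% (Wilson 7.20 to 17.40) and 4.67% (2.28 to 9.32), so d = 6.67. Lower = 6.67 − √(4.13² + 4.65²) = 0.4. Upper = 6.67 + √(6.07² + 2.39²) = 13.2.

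| Liquid v lyophilized, of 150 | Difference (95% CI), points | Exact CI, liquid | Exact CI, lyophilized |
|---|---|---|---|
| 7 v 7 | 0.0 (−5.2 to 5.2) | 1.9–9.4% | 1.9–9.4% |
| 14 v 7 | 4.7 (−1.3 to 10.9) | 5.2–15.2% | 1.9–9.4% |
| 17 v 7 | 6.7 (0.4 to 13.2) | 6.7–17.5% | 1.9–9.4% |
| 21 v 7 | 9.3 (2.8 to 16.2) | 8.9–20.6% | 1.9–9.4% |
| 22 v 7 | 10.0 (3.3 to 17.0) | 9.43–21.36% | 1.90–9.38% |

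The difference interval first excludes zero at 17 v 7. The exact per-arm intervals first separate at 22 v 7. At 21 v 7, a tripling, they still overlap.

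**2. Precision for ISRs.** No rate is available for two-device dosing, so equal rates are assumed. The half-width is 7.0 points at 10%, 9.1 at 20%, 10.3 at 30% and 11.0 at 40%.

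**3. Effect of persistent baseline positives.** Let a fraction b of each arm be positive at baseline and stay positive, with new-positive risks of 14/150 and 7/150 in the rest. The observed rate is b + (1 − b)p, so the difference shrinks by the factor (1 − b), while the ratio moves toward 1. The documents give no value of b; 2% and 5% are assumptions.

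| b | Difference, points | Ratio |
|---|---|---|
| 0% | 4.67 | 2.00 |
| 2% | 4.57 | 1.70 |
| 5% | 4.43 | 1.47 |

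**4. What an any-ISR difference can see.** Each subject receives one active and one placebo injection (Protocol 4.2), and the liquid placebo has the liquid product's pH and volumes (Protocol 6.1). With independent sites, the risk of any ISR is 1 − (1 − active risk of the assigned product)(1 − placebo risk of the other product). All per-site risks here are assumed.

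- *Vehicle or device effect of 10 points* (lyophilized placebo 5%, active 15%; liquid placebo 15%, active 25%). Liquid arm: 1 − 0.75 × 0.95 = 28.75%. Lyophilized arm: 1 − 0.85 × 0.85 = 27.75%. The any-ISR difference is 1.0 point; the active-site difference is 10.
- *Only the active liquid is worse* (liquid placebo 5%, active 25%). 28.75% v 1 − 0.85 × 0.95 = 19.25%. The any-ISR difference is 9.5 points; the active-site difference is 10.

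**The case against.** Descriptive safety reporting is a deliberate choice, applied consistently. The protocol asks for rates with 95% CIs and no inferential testing, and the SAP delivers that. The formal objective is to assess safety and tolerability, and the ADA and ISR sentence in Protocol 2.1 speaks of evaluation within the overall safety assessment. Counts by arm allow anyone to compute a difference, Listing 151 allows new positives to be identified, and the trial was not sized for these endpoints.

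Most of this stands as a limit on severity. A reader might infer that the SAP omits an analysis the protocol promised. It does not: nothing planned is contradicted. But a difference with a confidence interval is estimation, so it fits the no-testing rule, and a wide interval is still informative because it shows what has not been excluded. A reader who subtracts obtains a point estimate without an agreed numerator.

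Three stronger readings are tempting and fail.

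- *Persistent baseline positives seriously bias the comparison.* For the ratio they can; for the risk difference proposed here the effect is about 0.1 to 0.2 points in the illustration above, against an interval of about ±5.
- *A treatment-emergent definition makes the rate comparable with the historical figure of about 5%.* That figure comes from studies of up to 3 years, against 26 weeks here. The concurrent lyophilized arm is the comparator.
- *An ISR difference settles the pH and volume question raised in Protocol Table 2.* Under double-dummy dosing it can read about 1 point when the active-site difference is 10.

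**Conclusion.** The point holds as a cheap improvement to descriptive secondary safety reporting. It does not touch the HbA1c conclusion. No described ADA or ISR output estimates the difference between products, although the protocol frames the study as determining such differences. On-therapy ADA includes persistent baseline positives, and no treatment-emergent rule is described.

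The gain from a direct difference is concrete: against 7/150, its interval excludes zero at 17 positives rather than waiting for per-arm separation at 22. The gain from the baseline split is mainly in what the rate means and in any ratio.

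Assumptions: 150 evaluable subjects per arm, ADA near the historical level, and assumed ISR rates, per-site risks and baseline ADA prevalence. The absence of a subject-level baseline split is judged from text and titles, since the shells are not shown.

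**What to change.** Before unblinding:

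1. **SAP 8.2.3.** Define treatment-emergent ADA as baseline negative with at least one confirmed post-baseline positive, showing on-therapy and follow-up positives separately. Put baseline positives on their own row, reporting any titer rise in them. Put subjects with no baseline sample on a further row.
2. **SAP 8.2.2 and 8.2.3.** Report the liquid-minus-lyophilized risk difference with a 95% Newcombe or Miettinen-Nurminen CI and no p-value, for treatment-emergent ADA and for any on-therapy ISR per subject. Keep all per-arm displays.
3. **SAP 8.2.2.** State beside the ISR difference that both arms receive both devices and both vehicles, so it cannot by itself rule out pH, volume or device effects. If the eCRF records injector or site, add a version restricted to the active injection site.

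The cost is one definition, one caveat and a few rows in Tables 3.141 and 3.352, from data already planned. The downsides are the wide intervals, and that the active-site version depends on what the eCRF records.

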8.2.4. Adverse Events

All AEs will be coded using MedDRA which will be updated whenever available throughout the life of the study. Adverse events will be categorized by their occurrence in regard to therapeutic phase (pre-therapy, on-therapy, or post-therapy) as defined in [Appendix 4](#). Adverse events will be summarized in various subsets by treatment group. An overview summary of the number and percentage of subjects with any AE, the total number of AEs recorded, and the overall AE density and incidence rate for on-therapy AEs will be provided by treatment group. The overview will also summarize SAEs, treatment-related AEs, AEs by maximum intensity, and AEs by therapy phase.

Summaries of the number and percentage of subjects with any treatment-emergent AEs (TEAEs), related AEs, AEs leading to treatment discontinuation or withdrawal from study, SAEs, fatal AEs, will be provided. Adverse events will also be summarized by maximum intensity (mild, moderate, and severe).

AE summaries will not include hypoglycemic events, unless otherwise specified – The exceptions are summaries for serious AEs, AEs leading to withdrawal from treatment/study and pre-therapy AEs.

All AEs will be listed in a subject data listing.

